8.3.2.2 Subjects lost to follow-up

If a patient cannot be contacted to collect follow-up information even beyond the 10 days from visit 3, he/she will be considered "lost to follow-up". But before declaring that a patient is "lost to follow-up", the Principal Investigator (or his/her team) must do his/her best effort to contact patients and attempts should be made via all available routes. A certified letter should be sent to the permanent address on file.

The methods used to attempt to contact the patient should be noted in the patient medical file.

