- Number of family members in close contact developing common cold symptoms after the patient all over the study period.
- **Safety**: Assessment of adverse event/incidents/ undesirable expected side effects throughout the study.

Indication:

Treatment of acute rhinitis in children 6-10 years old

Investigation Design:

Prospective, open label, observational study

Visit 1 (V1) – (Day 1): Screening/Inclusion

Information and provision of the information sheet to legal guardians and participants, consent and assent signatures, demographic data and medical history, ongoing medication, physical and clinical examination, inclusion/non-inclusion criteria, record of patient choice regarding Healsea® Children use.

D1-D10 (at home):

Daily completion of the electronic diary (WURSS-K, adverse events/incident/undesirable expected side effects and concomitant medications, contamination of relatives if applicable, Healsea® Children daily administration if applicable).

D5±2 (at home): Telephone call 1

Investigator/nurse call to review patient status and study progress, adverse event/incident/undesirable expected side effects and concomitant treatments.

Visit 2 (V2) – (Day 10±2): End of treatment

End of Healsea® Children nasal spray treatment if applicable, assessment of symptoms, diary review, reporting of adverse events/incident/undesirable expected side effects.

D11-D30±5 (at home):

Daily completion of the diary (Adverse event, concomitant medications, contamination of relatives if applicable, WURSS-K if applicable, until the subject feels not sick for two consecutive days).

D20±2 (at home): Telephone call 2

Investigator/nurse call to review patient status and study progress, adverse events and concomitant treatments.

Version: **2.0**; **08** Sep **2021** Page **16** of **61** Study Number: **LPH-2101**

	Visit 3 (V3) – (Day 30±2): End of study					
	Physical and clinical examination, diary review, reporting of adverse events and					
	concomitant treatments.					
Number of Subjects:	15 centers will be involved in this study. We plan to follow a cohort of 200					
	subjects . The recruitment will be competitive in both group, exposed to					
	Healsea® Children or not exposed to Healsea® Children. However, when 100					
	patients will be recruited in one group, the recruitment will be stopped in this					
Towart Downlotions	group but will continue in the other group until 100 patients to be enrolled.					

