The Investigator or his/her delegated designee will call the patient to review patient status and study progress, adverse event, and concomitant treatments.

Visit 3 (V3) – (Day 30±5): end of study

The investigator or his/her delegated designee will:

- Perform a physical and clinical examination,
- Record the common cold symptoms if they persist,
- Validate the adverse events and concomitant medications reported in the e-CRF through the e-diary and report any new relevant safety event.

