3. STUDY DESIGN

This is a prospective, open label, interventional, national (Poland), multicentric study. During this prospective interventional study, one cohort of IgE-dependent allergic children with early symptoms of infectious rhinitis will be followed, children being treated with Healsea® Children on top of common cold conventional therapies or with conventional therapies only (nasal irrigation excepted). This study aimed to confirm the benefit of Healsea® Children in a real life setting in children with perennial allergy.

Investigational plan description (see Figure 1):

- **Visit 1 (V1) – (Day 1): Screening/Inclusion**

Information and provision of the information sheet to legal guardians and participants, consent and assent signatures, demographic data and medical history, ongoing medication, physical and clinical examination, inclusion/non-inclusion criteria, record of patient choice regarding Healsea® Children use.

- **D1-D10 (at home):**

Daily completion of the electronic diary (WURSS-K, adverse events/incident/ undesirable expected side effects and concomitant medications, contamination of relatives if applicable, Healsea® Children daily administration if applicable).

– **D5±2 (at home): Telephone call 1**

Investigator/nurse call to review patient status and study progress, adverse event/incident/undesirable expected side effects and concomitant treatments.

– **Visit 2 (V2) – (Day 10±2): End of treatment**

End of Healsea® Children nasal spray treatment if applicable, assessment of symptoms, diary review, reporting of adverse events/incident/undesirable expected side effects.

– **D11-D30±5 (at home):**

Daily completion of the diary (Adverse event, concomitant medications, contamination of relatives if applicable, WURSS-K if applicable, until the subject feels not sick for two consecutive days).

– **D20±2 (at home): Telephone call 2**

Investigator/nurse call to review patient status and study progress, adverse events and concomitant treatments.

– **Visit 3 (V3) – (Day 30±5): End of study**

Physical and clinical examination, diary review, reporting of adverse events and concomitant treatments

The maximal study duration for each subject is 35 days.

Visit name	ACUTE PHASE				FOLLOW-UP		
	Screening/Inclusion	At home	Telephone call	End of treatment	At home	Telephone call	End of study
Visit Number	V1		TC1	V2		TC2	V3
Days/Weeks	D1	D1 – D10	D5±2	D10±2	D11 – D30±5	D20±2	D30 ± 5
Screening and General Assessments							

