6.4. General conventions and calculated variables**6.4.1. Subject reference start/end dates**

For each subject, the reference dates will be the following:

- The reference start date is the date of inclusion visit.
- The reference end date is the date when subject was determined to have ended the trial.

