6.4.4. Missing start/end dates of adverse events / incidents / expected side effects

In the following paragraphs, adverse events, incidents and expected side effects will be referred to as “adverse events” for ease of reading.

a) Start date

Completely missing date: it will be estimated by the reference start date.

If the day and the month are missing:

- If the year = year of reference start date, it will be estimated by the reference start date
- If the year < year of reference start date, it will be estimated by the 31st December
- If the year > year of reference start date, it will be estimated by the 1st January

If only the day is missing:

- If the month/year = month/year of reference start date, it will be estimated by the date of reference start date
- If the month/year < month/year of reference start date, it will be estimated by the last day of the month
- If the month/year > month/year of reference start date, it will be estimated by the first day of the month

If after imputation, the estimated start date is after the end date of the adverse event, it will be replaced by the end date of the adverse event.

b) End date

Note: the following rules concern events that are not “ongoing” at the end of the study.

Completely missing date: it will be estimated by the reference end date

If the day and the month are missing:

- If the year = year of reference end date, it will be estimated by the reference end date
- If the year < year of reference end date, it will be estimated by the 31st December
- If the year > year of reference end date, it will be estimated by the 1st January

If only the day is missing:

- If the month/year = month/year of reference end date, it will be estimated by the reference end date
- If the month/year < month/year of reference end date, it will be estimated by the last day of the month
- If the month/year > month/year of reference end date, it will be estimated by the first day of the month

If after imputation, the estimated end date is before the start date of the adverse event, it will be replaced by the start date of the adverse event.

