11.1. Study duration

Study duration will be calculated according to the formula below:

$$\text{Study duration (days)} = \text{Reference End Date} - \text{Reference Start Date} + 1$$

It will be described (see §6.2) on the FAS.

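### On the natural reading of the SAP, a child lost to follow-up at any time gets a study end of about D36 to D46, so symptom-duration censoring falls at D30 instead of the last diary day

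*Protocol*

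**What the plan says.** Protocol 8.3.2.2 counts from Visit 3, not from the last contact: "If a patient cannot be contacted to collect follow-up information even beyond the 10 days from visit 3, he/she will be considered" lost to follow-up. It gives no other trigger and asks for tracing by all available routes first. Visit 3 is due at D25 to D35 in the body of the protocol ("Visit 3 (V3) – (Day 30±5): end of study"), in both flow charts and in SAP section 3. The protocol synopsis gives a narrower window ("Visit 3 (V3) – (Day 30±2): End of study").

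SAP 6.4.1 says: "The reference end date is the date when subject was determined to have ended the trial". It has no separate rule for children who are lost. That date is then used in four places:

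- SAP 11.1 computes study duration from it ("Study duration will be calculated according to the formula below"), for Table 14.1.4.
- SAP 10.2.2 censors a child whose last answer on a symptom was positive, and who has no recovery date, at D30 or at the reference end date, taking the earlier.
- SAP 6.4.4 uses it to impute end dates of adverse events that are not ongoing: "Completely missing date: it will be estimated by the reference end date".
- SAP 6.4.5 applies the same imputation to concomitant medications.

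SAP section 3 also says: "The maximal study duration for each subject is 35 days".

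**The concern.** A child who stops responding in the first week cannot be declared lost until after the Visit 3 window plus the tracing period. If the date of that declaration is the reference end date, the child is recorded as followed for longer than a child who attended every visit.

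The Cox models of symptom duration are where this matters most. Taking the earlier of D30 and the end of study should stop a child's time at risk when observation stops. For a lost child the second date is always later than D30, so it never applies. A child lost while symptomatic then stays in the risk set, apparently unrecovered, to D30. This makes recovery look slower in whichever group loses more children. Treatment is open-label and chosen by the family, so there is no reason to assume equal loss in the two groups.

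Two lesser effects follow. Table 14.1.4, the planned summary of observation time by group, moves the wrong way, because more loss raises the mean. Also, a medication with a wholly missing end date can be run on past the last contact and counted as used up to D30.

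**Working it through.** **Inputs**

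- Day 1 is the inclusion visit (SAP 6.4.1: "The reference start date is the date of inclusion visit").
- Duration = later date − earlier date + 1 (SAP 6.4.2 and 11.1).
- Visit 3 is due at D25 to D35, or D28 to D32 in the protocol synopsis.
- The earliest declaration of loss is the first day more than 10 days after Visit 3, so Visit 3 day + 11.
- Assumption: for a child with no Visit 3, the rule counts from the day on which it was due.

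**The plan's own figure.** The latest Visit 3 is D30 + 5 = D35, and 35 − 1 + 1 = 35 days. The stated maximum reproduces.

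**Step 1. Study duration if the declaration date is the end date**

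| Visit 3 due | Completer | Declared at +10 | First day beyond (+11) |
|---|---|---|---|
| D25 | 25 | 35 | 36 |
| D28 | 28 | 38 | 39 |
| D30 | 30 | 40 | 41 |
| D32 | 32 | 42 | 43 |
| D35 | 35 | 45 | 46 |

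Every value in the last column exceeds 35. Even with declaration at exactly 10 days, only the D25 row does not exceed 35.

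**Step 2. Effect by day of last contact** (Visit 3 due D30, last diary entry on the day of last contact)

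| Last contact | Duration as written | Excess over last contact | Cox censoring day | Unobserved days at risk (30 − last day) |
|---|---|---|---|---|
| D2 | 41 | 39 | D30 | 28 |
| D5 | 41 | 36 | D30 | 25 |
| D10 | 41 | 31 | D30 | 20 |
| D20 | 41 | 21 | D30 | 10 |
| D29 | 41 | 12 | D30 | 1 |

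The duration is the same in every row. Only the excess depends on when contact ended. Censoring is the earlier of 30 and 41, so always D30. The same holds for every window in Step 1, since the smallest value there for a lost child is 35.

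**Step 3. Mean study duration.** The documents give no loss rate, so these are assumed cases: 100 children, completers ending at D30, k lost. As written, the mean is ((100 − k) × 30 + k × 41)/100. By last contact at day L, it is ((100 − k) × 30 + k × L)/100.

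- k = 5, L = 5: 30.55 against 28.75 days.
- k = 10, L = 5: 31.10 against 27.50 days.
- k = 5, L = 20: 30.55 against 29.50 days.

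**Step 4. Medication days.** Take a medicine started at D1, not ongoing, with a wholly missing end date, in a child last contacted at D5. As written, the imputed end is after D30, so the D1–D30 count in SAP 10.2.4 is 30 − 1 + 1 = 30 days. By last contact it is 5 − 1 + 1 = 5 days.

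**The case against.** The strongest objection is that SAP 6.4.1 never mentions loss to follow-up. Protocol 8.3.2.2 says when the label may be applied, not when the child's study ended. The end date of a lost child might be left missing, and SAP 6.4.3 would then have the Validation Committee extrapolate it from all the information recorded, which would include the diary. It is true that equating the two dates is an inference. But 6.4.1 speaks of a determination and not of a last observation, and the fallback applies only when the date is missing. Even then it states no last-contact rule. Either way the date needs defining.

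It can also be said that the 35 days describe scheduled participation, and that tracing is not participation. That is a fair account of the figure's origin, but SAP 11.1 would still report durations above it under nearly the same name.

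The effect is limited. Under SAP 6.3.1 only the primary criterion is conclusive, and Table 14.1.4 is descriptive. With few or late losses the shift in the mean is about one day.

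A reader might infer more than the documents support:

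- *That children lost earliest get the longest durations.* They do not. All lost children share the same floor, and only the overstatement is larger for early losses.
- *That the end-of-study limb of the censoring rule never works.* It still works for withdrawn children, who have a premature end-of-study visit (protocol 8.3.2.1), and for completers with Visit 3 at D25 to D29.
- *That the adverse-event tables are distorted.* They count subjects and events and use no event durations.

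**Conclusion.** The point holds as a defect in secondary and descriptive outputs. On the natural reading, any child lost to follow-up gets a study duration of at least about 36 to 46 days (39 to 43 with the synopsis window). This is above the 35-day maximum and above every completer seen within the window. The consequence that matters is in the six Cox models of symptom duration, where a child lost while symptomatic and without a recovery date is censored at D30. That adds from 1 unobserved day at risk (last seen D29) to 28 (last seen D2).

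The primary AUC does not use the reference end date and is unaffected. The result rests on two assumptions: that the declaration of loss is the determination meant in SAP 6.4.1, and that Visit 3 means its due date when the visit did not take place. The effect on the hazard ratios depends on how many children are lost, when, and how unequally between groups. The documents give none of these, so I put no figure on it.

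**What to change.** In SAP 6.4.1, add that for children lost to follow-up the reference end date is the date of the last recorded contact (diary entry, telephone call or visit). In SAP 10.2.2, censor such children at the earlier of D30 and their last completed diary day, and state that the carrying forward of missing answers in that section stops on the same day. Record the date of the lost-to-follow-up declaration separately from the date of last contact. The two Visit 3 windows in the protocol should be reconciled at the same time.

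The tracing period in protocol 8.3.2.2 can stay as it is, since shortening it could class reachable children as lost. A D35 cap on the reference end date is not needed and would misdate a child genuinely contacted later.

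The cost is two short SAP additions and one separately recorded date. Reported mean study duration and time at risk become slightly shorter.

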8.3.2.3 Subject replacement

It is not anticipated to replace withdrawal patients.

8.3.3 Point of enrolment

The subjects will be recruited by the sites among outpatients coming in consultation because of early symptoms of common cold.

Version: **2.0**; **08** Sep **2021** Page **33** of **61**

To facilitate the enrolment, parents/legal guardians of allergic children coming for routine consultation will be informed of this clinical trial. In case of the onset of acute infectious rhinitis/rhinosinusitis symptoms, they will be invited to contact the site and to come for a consultation if they are interested. Before performing any study procedure, the investigator will give all the information pertaining to the study and the patient's legal guardians will sign the consent form if they accept their child study participation. Children will also receive an information specific to their age and will be invited to sign an assent presented by the investigator.

8.3.4 Total expected duration of the clinical investigation

The total study duration is planned to be 4 months.

8.3.5 Expected duration of each subject's participation

The duration of each patient's participation is 30 days.

8.3.6 Number of subjects required to be included in the clinical investigation

A cohort of 200 children is expected to participate in the study.

8.3.7 Estimated time needed for the enrolment

It is expected to enrol a cohort of 200 patients within 3 months.

8.3.8 Relationship of investigation population to target population

Healsea® Children will be used within its intended use. This observational study aimed to confirm the benefit of Healsea® Children in a real life setting in children with perennial allergy and early symptoms of infectious rhinitis.

8.3.9 Vulnerable, pregnant and breastfeeding population

Patient under tutorship or legal guardianship are not eligible.

Pregnant and breastfeeding women: not applicable because it is a paediatric observational study.

8.3.10 Compensation

No compensation is planned because this is an observational study. Travel expenses will be reimbursed in full on presentation of receipts attesting to such expenses for visits 2 and 3, considering that visit 1 is a routine care consultation.

8.3.11 Study procedures

The study will comprise 3 visits and 2 telephone calls.

Version: **2.0**; **08** Sep **2021** Page **34** of **61**

Visit 1 (V1) - (Day 1): Screening/Inclusion

The investigator will give oral information relative to the study to parents/legal guardians and the participant. If both parents/legal guardians agree that their child participate in the study, they will receive the information sheet and will be also asked to give a written consent. In case one parent will not be available for the visit; he/she will be asked to confirm in writing that he/she agrees with the participation of the child in the study. Children will also receive an information specific to their age and will be invited to sign an assent by the investigator.

Each screened subject will be assigned a subject identifier number during screening. The subject identifier number will contain the site number and the subject number and will be assigned in numerical order at the screening visit based on chronological order of screening dates (e.g., 01-010 for the 10th subject screened at the Site #01).

The investigator or his/her delegated designee will:

- Record demographic data and medical history and ongoing medication,
- Perform a physical and clinical examination,
- Record the score of the common cold symptoms (headache, muscle ache, chilliness, sore throat, blocked nose, runny nose, cough, sneezing according a physician-rated symptom score after clinical examination of the child; (scale: 0 3 [0: no symptom, 1 = mild symptoms (sign/symptom clearly present, but minimal awareness; easily tolerated), 2 = moderate symptoms (definite awareness of sign/symptom that is bothersome but tolerable), 3 = severe symptoms (sign/symptom that is hard to tolerate; causes interference with activities of daily living and/or sleeping]). This scoring system was developed by Jackson in 1958 and is widely used in common cold clinical trials [19],
- Verify that eligibility criteria are fulfilled,
- Record the patient choice regarding Healsea® Children use (if the patient/parents choose nasal symptoms to be treated with Healsea® Children, instructions will be given to the patient/parents for getting the test product at the end of the visit),
- Explain to the child/parents/legal guardians how to use Healsea® Children if applicable,
- Review and detail the questions of the WURSS-K,
- Explain how to use the e-diary for WURSS-K recording, how to report adverse events/
 incidents/expected undesirable side effects, concomitant medications, and contamination of
 relatives in the e-diary. The legal guardians will access the e-diary website
 (https://me.vieodoc.net) using a smartphone and logging in with a randomly assigned
 username and Pin code. Data recorded in the e-diary will be at the same time uploaded in the
 e-CRF.

D1-D10 (at home):

The patients will be asked to complete the electronic diary daily (WURSS-K assessed once daily in the evening, taking in account the symptoms from the morning to the evening, adverse events/incidents/expected undesirable side effects and concomitant medications, contamination of relatives) and to report Healsea® Children intake if applicable. For the Healsea® Children treated-group, compliance will be indirectly assessed by the question: "do you use the nasal spray as

Version: **2.0**; **08** Sep **2021** Page **35** of **61** Study Number: **LPH-2101**

recommended (1 puff 2 sec in each nostril twice a day)?". If necessary, the parent(s) will help their child in this task.

D5 (Day 5±2, at home): Telephone call 1

The Investigator or his/her delegated designee will call the patient to review patient status and study progress, adverse event/incidents/expected undesirable side effects and concomitant treatments.

Visit 2 (V2) - (Day 10±2): end of treatment

The investigator or his/her delegated designee will:

- Perform a physical and clinical examination,
- Record the common cold symptoms if they persist,
- Validate the adverse events/incidents/expected undesirable side effects and concomitant medications reported in the e-CRF through the e-diary and report any new relevant safety event.

For patients receiving Healsea® children, the treatment will be stopped at D10. The patients for whom common cold symptoms persist, will be instructed to continue to score the WURSS-K until the subject feels not sick for two consecutive days.

D11-D30 (at home):

After D10, the WURSS-K will be assessed once daily until the subject feels not sick for two consecutive days if applicable. The patients will be asked to complete the electronic diary daily (WURSS-K if applicable, adverse events, concomitant medications, and contamination of relatives). If necessary, the parent(s) will help their child in this task.

D20 (Day 20±2, at home): Telephone call 2

The Investigator or his/her delegated designee will call the patient to review patient status and study progress, adverse event, and concomitant treatments.

Visit 3 (V3) – (Day 30±5): end of study

The investigator or his/her delegated designee will:

- Perform a physical and clinical examination,
- Record the common cold symptoms if they persist,
- Validate the adverse events and concomitant medications reported in the e-CRF through the e-diary and report any new relevant safety event.

